3.3 SELECTION OF TRIAL POPULATION

It is planned that 88 healthy male subjects will enter the study. The actual number of subjects entered may exceed the total of 88 if additional intermediate doses will be tested (see [Section 3.1](#)) but will not exceed 104 subjects entered. Subjects will be recruited from the volunteers' pool of the trial site.

Only male subjects will be included into the study because hitherto no data on reproductive toxicology are available. With respect to the embryo-fetal risk derived from the treatment of male subjects with BI 473494, where it is theoretically possible that relevant exposure to BI 473494 may be achieved in women of child-bearing potential (WOCBP) from exposure to seminal fluid, male contraception (condom or sexual abstinence) should be used in order to avoid exposure of an existing embryo/fetus [[R16-0373](#)] (see [Section 3.3.3](#), exclusion criterion 23).

A log of all subjects enrolled into the trial (i.e. having given informed consent) will be maintained in the ISF at the investigational site irrespective of whether they have been treated with investigational drug or not.

3.3.1 Main diagnosis for study entry

The study will be performed in healthy subjects.

3.3.2 Inclusion criteria

Subjects will only be included into the trial, if they meet the following criteria:

1. Healthy male subjects according to the assessment of the investigator, based on a complete medical history including a physical examination, vital signs (BP, PR), 12-lead ECG, and clinical laboratory tests
2. Age of 18 to 45 years (incl.)
3. BMI of 20.0 to 29.9 kg/m² (incl.)
4. Signed and dated written informed consent prior to admission to the study in accordance with GCP and local legislation

Proprietary confidential information © 2017 Boehringer Ingelheim International GmbH or one or more of its affiliated companies

3.3.3 Exclusion criteria

Subjects will not be allowed to participate if any of the following general criteria apply:

1. Any finding in the medical examination (including BP, PR or ECG) is deviating from normal and judged as clinically relevant by the investigator
2. Repeated measurement of systolic blood pressure outside the range of 90 to 140 mmHg, diastolic blood pressure outside the range of 50 to 90 mmHg, or pulse rate outside the range of 50 to 90 bpm
3. Any laboratory value outside the reference range that the investigator considers to be of clinical relevance
4. Any evidence of a concomitant disease judged as clinically relevant by the investigator
5. Gastrointestinal, hepatic, renal, respiratory, cardiovascular, metabolic, immunological or hormonal disorders
6. Cholecystectomy and/or surgery of the gastrointestinal tract that could interfere with the pharmacokinetics of the trial medication
 - except appendectomy and simple hernia repair
7. Diseases of the central nervous system (including but not limited to any kind of seizures or stroke), and other relevant neurological or psychiatric disorders
8. History of relevant orthostatic hypotension, fainting spells, or blackouts
9. Chronic or relevant acute infections
10. History of relevant allergy or hypersensitivity (including allergy to the investigational trial medication
11. Use of drugs within 30 days prior to administration of trial medication if that might reasonably influence the results of the trial (incl. QT/QTc interval prolongation)
12. Participation in another trial where an investigational drug has been administered within 60 days prior to planned administration of trial medication, or current participation in another trial involving administration of investigational drug
13. Smoker (more than 10 cigarettes or 3 cigars or 3 pipes per day)
14. Inability to refrain from smoking on specified trial days
15. Alcohol abuse (consumption of more than 30 g per day)
16. Drug abuse or positive drug screening
17. Blood donation of more than 100 mL within 30 days
 - intended donation during the trial

or
18. Intention to perform excessive physical activities within 4 days
 - or during the trial
19. Inability to comply with dietary regimen of trial site
20. A marked baseline prolongation of QT/QTc interval (such as QTc intervals that are repeatedly greater than 450 ms) or any other relevant ECG finding at screening
21. A history of additional risk factors for Torsades de Pointes (such as heart failure, hypokalaemia, or family history of Long QT Syndrome)

Proprietary confidential information © 2017 Boehringer Ingelheim International GmbH or one or more of its affiliated companies

22. Subject is assessed as unsuitable for inclusion by the investigator, for instance, because considered not able to understand and comply with study requirements, or has a condition that would not allow safe participation in the study

In addition, the following trial-specific exclusion criteria apply:

23. Male subjects with WOCBP partner who are unwilling to use male contraception (condom or sexual abstinence) from administration of investigational trial medication until 30 days after administration of investigational trial medication

24.

25. Known maltose intolerance / maltose malabsorption

26. Laboratory values outside the reference range for ALT, AST, total bilirubin, fasting plasma glucose or HbA1c.

For study restrictions, refer to [Section 4.2.2](#).

3.3.4 Removal of subjects from therapy or assessments

3.3.4.1 Removal of individual subjects

An individual subject is to be removed from the trial if:

1. The subject withdraws consent for trial treatment or trial participation, without the need to justify the decision
2. The subject needs to take concomitant drugs that interfere with the investigational product or other trial medication
3. The subject is no longer able to participate for other medical reasons (such as surgery, adverse events (AEs), or diseases)
4. An AE or clinically significant laboratory change or abnormality occurred that the Investigator judges to warrant discontinuation of treatment. This may include cases of sustained symptomatic hypotension or hypertension or clinically relevant changes in ECG requiring intervention.
5. The subject shows an elevation of AST and/or ALT ≥ 3 -fold ULN combined with an elevation of total bilirubin ≥ 2 -fold ULN (measured in the same blood sample) and/or needs to be followed up according to the 'DILI checklist' provided in the ISF.

In addition to these criteria, the physician may discontinue subjects at any time based on his or her clinical judgment.

A subject can also be removed from the trial if eligibility criteria are being violated or if the subject fails to comply with the protocol (for instance, by non-adherence to dietary rules, or non-attendance at study assessments).

If a subject is removed from or withdraws from the trial prior to first administration of investigational trial medication , the data of this subject will not be entered in the

Proprietary confidential information © 2017 Boehringer Ingelheim International GmbH or one or more of its affiliated companies

case report form (CRF) or trial database and will not be reported in the clinical trial report (CTR). If a subject is removed from or withdraws from the trial after first administration of investigational trial medication [REDACTED], this will be documented and the reason for discontinuation must be recorded in the CRF. In this case, the data will be included in the CRF/trial database and will be reported in the CTR. At the time of discontinuation a complete end of trial examination will be performed if possible and the information will be recorded in the CRFs. These discontinuations will be discussed in the CTR.

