Main criteria for inclusion: Healthy male subjects, age of 18 to 45 years (inclusive), body mass index (BMI) of 20.0 to 29.9 kg/m ² (inclusive)				
Test products: BI 473494 solution for injection (1 mg/mL and 10 mg/mL) dose: 35 µg - 75 µg - 150 µg - 300 µg - 550 µg - 1.0 mg - 1.6 mg - 2.6 mg - 4.0 mg - 6.0 mg - 8.5 mg mode of admin.: Subcutaneous (SC) injection				
Comparator product: Placebo (isotonic sodium chloride solution) dose: Not applicable mode of admin.: SC injection				
Duration of treatment: Single dose				

Proprietary confidential information © 2017 Boehringer Ingelheim International GmbH or one or more of its affiliated companies

Name of company: Boehringer Ingelheim		Tabulated Trial Protocol		
Name of finished product: Not applicable				
Name of active ingredient: BI 473494				
Protocol date: 02 May 2017	Trial number: 1400-0001		Revision date: Not applicable	
Criteria for safety: Primary endpoint to assess safety and tolerability of BI 473494 is the number [N (%)] of subjects with drug-related adverse events (AEs). Further criteria of interest: 
• AEs including clinically relevant findings from the physical examination, safety laboratory tests, 12-lead electrocardiogram (ECG), vital signs (blood pressure [BP], pulse rate [PR])				
Criteria for pharmacokinetics: Secondary endpoints: AUC _{0-tz} and C _{max} of BI 473494				
Criteria for pharmacodynamics:				
Statistical methods: Descriptive statistics will be calculated for all endpoints. Dose proportionality of BI 473494 will be explored using a regression model. A 95% confidence interval (CI) for the slope will be computed.				

Proprietary confidential information © 2017 Boehringer Ingelheim International GmbH or one or more of its affiliated companies

FLOW CHART

Visit	Day	Planned time (relative to trial activities ¹⁷ [h:min])	Approximate clock time of actual day [h:min]	Event and comment	Safety laboratory	PK _{urine} ^{10,12,13}	12-lead ECG	Vital signs (BP, PR)	Questioning for AEs and concomitant therapy ⁶
1	-21 to -2			Screening (SCR) ¹	x				
2	-1	-24:00	08:00	Ambulatory visit ⁷	x ⁷		x	x	x
		-12:30	18:30	Admission to trial site	x ¹⁵		x ⁷	x ⁷	x
		-12:00	19:00	Dinner					
	1	-0:45 ²	06:15	Allocation to subject number				x	x
		-0:10	06:50						
		0:00*	07:00						
		0:15	07:15						
		0:30	07:30						
		0:45	07:45						
		1:00	08:00					x	x
		1:30	08:30					x	x
		2:00	09:00	240 mL fluid intake					
		3:00	10:00						

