1. Subject must be informed and written informed consent obtained prior to starting any screening procedures. Screening procedures include physical examination, check of vital signs, ECG, safety laboratory (including drug screening), demographics (including determination of body height and weight, smoking status and alcohol history), relevant medical history, concomitant therapy and review of inclusion/exclusion criteria.
2. The time is approximate; the respective procedures are to be performed and completed within 2 h prior to administration of BI 473494 or placebo in Visit 3. Allocation to treatment may be performed at any time following enrolment but must be completed prior to
3. If several actions are indicated at the same time point, the intake of meals or liquids will be the last action.
4. End of trial examination includes physical examination, body weight, vital signs, ECG, safety laboratory, recording of AEs and concomitant therapies.
6. AEs and concomitant therapies will be recorded throughout the trial, but will be specifically asked for at the time points indicated in the [Flow Chart](#) above.
7. Safety laboratory to be taken and to be medically evaluated within 3 days prior to
This safety lab will not include drug screening or alcohol breath test. The ambulatory visit can be omitted, if the screening examination is performed on Days -3 or -2.
8. In addition, two blood samples for stability testing will be taken at this point in DG 6 (1.0 mg), (refer to [Section 5.5.2.6](#)).
9. The ECG recording has to be performed as triple at this time point.
10. Sampling times and periods may be adapted based on information obtained during the trial (e.g. preliminary PK data), including addition of samples and visits as long as the total blood volume taken does not exceed 500 mL per subject.
11. Including blood sample for metabolite identification only in DG 6 (1.0 mg), (refer to [Section 5.5.2.2](#)).
12. A blank urine sample (x) is to be obtained prior to administration of trial medication. Other urine samples are to be collected over the stated post-dose intervals (◀—|—|→) 0-12, 12-24, 24-48 and 48-72h.
13. Urine sampling will be performed from DG 5 (550 µg) onwards.
14. On Days 5-29, a deviation from the scheduled time of \pm 70 min is acceptable for all the planned trial activities.

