5.2.2.2 Adverse event collection and reporting

AEs collection

Upon enrolment into a trial, the subject's baseline condition is assessed (for instance, by documentation of medical history/concomitant diagnoses), and relevant changes from baseline are noted subsequently.

Subjects will be required to report spontaneously any AEs as well as the time of onset, end, and intensity of these events. In addition, each subject will be regularly assessed by the medical staff throughout the clinical trial and whenever the investigator deems necessary. As a minimum, subjects will be questioned for AEs (and concomitant therapies) at the time points indicated in the [Flow Chart](#). Assessment will be made using non-specific questions such as 'How do you feel?'. Specific questions will be asked wherever necessary in order to more precisely describe an AE.

[figure not shown]
A careful written record of all AEs shall be kept by the investigator in charge of the trial. Records of AEs shall include data on the time of onset, end time, and intensity of the event as well as any treatment or action required for the event and its outcome.

The following must be collected and documented on the appropriate CRF(s) by the investigator:

- From signing the informed consent onwards until an individual subject's end of trial:
 - All AEs (serious and non-serious) and all AESIs.
 - The only exception to this rule are AEs (serious and non-serious) and AESIs in Phase I trials in healthy volunteers, when subjects discontinue from the trial due to screening failures prior to administration of any trial medication. In these cases, the subjects' data must be collected at trial site but will not be entered in the CRF or trial database and will not be reported in the CTR.
- After the individual subject's end of trial:

Proprietary confidential information © 2017 Boehringer Ingelheim International GmbH or one or more of its affiliated companies

- The investigator does not need to actively monitor the subject for AEs but should only report related SAEs and related AESIs of which the Investigator may become aware of by any means of communication, e.g. phone call. Those AEs should, however, not be reported in the CRF.

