The REP for BI 473494, when measurable drug levels or PD effects are still likely to be present after the last administration, is not known for this first-in-human trial. Therefore, all AEs reported until the end of trial examination (last per protocol contact) will be considered on treatment; please see [Section 7.3.3](#).

AE reporting to sponsor and timelines

The Investigator must report SAEs, AESIs, and non-serious AEs which are relevant for the reported SAE or AESI, on the BI SAE form via fax immediately (within 24 hours) to the Sponsor's unique entry point (country specific contact details will be provided in the ISF). The same timeline applies if follow-up information becomes available. In specific occasions the Investigator could inform the Sponsor upfront via telephone. This does not replace the requirement to complete and fax the BI SAE form.

With receipt of any further information to these events, a follow-up SAE form has to be provided. For follow-up information the same rules and timeline apply as for initial information.

Information required

For each AE, the Investigator should provide the information requested on the appropriate CRF pages and the BI SAE form, if applicable. The Investigator should determine the causal relationship to the trial medication and any possible interactions between the trial medication

The following should also be recorded as an (S)AE in the CRF and BI SAE form (if applicable):

- Worsening of the underlying disease or of other pre-existing conditions

Proprietary confidential information © 2017 Boehringer Ingelheim International GmbH or one or more of its affiliated companies

- Changes in vital signs, ECG, physical examination and laboratory test results, if they are judged clinically relevant by the Investigator.

If such abnormalities already pre-exist prior to trial inclusion they will be considered as baseline conditions and should be collected in the eCRF only.

All (S)AEs, including those persisting after individual subject's end of trial must be followed up until they have resolved, have been assessed as 'chronic' or 'stable', or no further information can be obtained.

Hypoglycaemia

Hypoglycaemic events will be recorded as AEs if symptomatic, or if plasma glucose levels are below 54 mg/dL (in safety laboratory) or blood glucose levels are below 49 mg/dL (in bedside test).

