6.2.4 Visit 4 - End of trial period

For AE assessment, laboratory tests, recording of ECG and vital signs, and physical examination during the end of trial period, see [Sections 5.2.2](#) to [5.2.5](#).

Proprietary confidential information © 2017 Boehringer Ingelheim International GmbH or one or more of its affiliated companies

Subjects who discontinue treatment before the end of the planned treatment period should undergo the end of trial visit.

All abnormal values (including laboratory parameters) that are judged clinically relevant by the investigator will be monitored using the appropriate tests until a return to a medically acceptable level is achieved. (S)AEs persisting after subject's end of trial must be followed up until they have resolved, have been sufficiently characterized, or no further information can be obtained.

The end of the trial as a whole is defined by the 'last regular visit completed by last subject' or 'end date of the last open AE' or 'date of the last follow-up test' or 'date of an AE has been decided as sufficiently followed-up', whichever is latest.

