7. PLANNED ANALYSIS

The placebo group in the safety evaluation will consist of all placebo treated subjects, regardless of the dose group in which they were treated.

Safety analysis (refer to [Section 7.8](#)) will be performed by and will be presented in Sections 15.1 to 15.4 of the CTR and in Appendix 16.2 and 16.1.13.1.

Descriptive data analysis of PK parameters and concentrations will be performed by the department Translational Medicine and Clinical Pharmacology (TMCP) at BI and will be presented in Section 15.6 and 15.7 of the CTR.

The format of the listings and tables will follow the standards defined in the BI corporate guideline “Reporting of Clinical Trials and Project Summaries” [001-MCG-159] ([6](#)) with the exception of those generated for PK-calculations.

The individual values of all subjects will be listed, sorted by treatment group, subject number, and visit.

The listings will be included in Appendix 16.2 of the CTR.

For end-of-text tables, the set of summary statistics for non-PK parameters is:

N	number non-missing observations
Mean	arithmetic mean
SD	standard deviation
Min	minimum
Median	median
Max	maximum

For analyte concentrations, the following descriptive statistics will additionally be calculated:

CV	arithmetic coefficient of variation
gMean	geometric mean
gCV	geometric coefficient of variation

For PK parameters, the following descriptive statistics will additionally be calculated:

CV	arithmetic coefficient of variation
gMean	geometric mean
gCV	geometric coefficient of variation
P10	10th percentile
Q1	1st quartile
Q3	3rd quartile
P90	90th percentile

The data format for descriptive statistics of concentrations will be identical with the data format of the respective concentrations. The descriptive statistics of PK parameters will be calculated using the individual values with the number of decimal places as provided by the evaluation program. Then the individual values as well as the descriptive statistics will be reported with three significant digits in the CTR.

Tabulations of frequencies for categorical data will include all possible categories and will display the number of observations in a category, as well as the percentage (%) for each treatment group. Percentages will be rounded to one decimal place and will be based on all subjects in the respective subject set whether they have non-missing values or not. The category 'missing' will be displayed only if there are actually missing values.

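### Removal after the single injection brings the end-of-trial examination forward, and no text keeps the subject on the remaining AE, ECG, laboratory and PK schedule

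*Protocol*

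**What the plan says.** The synopsis gives "Duration of treatment: Single dose". Protocol 3.3.4.1 lists reasons for which a subject is to be removed from the trial. Criterion 4 reads: "An AE or clinically significant laboratory change or abnormality occurred that the Investigator judges to warrant discontinuation of treatment". Criterion 5, the hepatic alert, carries no such judgement clause. The consequence of removal is stated once for all reasons: "At the time of discontinuation a complete end of trial examination will be performed if possible". Protocol 6.2.4 adds: "Subjects who discontinue treatment before the end of the planned treatment period should undergo the end of trial visit".

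Flow Chart footnote 4 defines that visit: "End of trial examination includes physical examination, body weight, vital signs, ECG, safety laboratory, recording of AEs and concomitant therapies". No PK sample is listed. SAP 6.7 makes the end-of-trial ECG a single recording without central evaluation.

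Protocol 5.2.2.2 collects all AEs in the CRF up to the individual's end of trial. After that, "The investigator does not need to actively monitor the subject for AEs but should only report related SAEs and related AESIs", and these do not go into the CRF. For analysis, "all AEs reported until the end of trial examination (last per protocol contact) will be considered on treatment". SAP 6.1 closes the on-treatment phase at midnight following the trial termination date. The removed subject stays in the Treated Set, and under SAP 7 percentages "will be based on all subjects in the respective subject set whether they have non-missing values or not". Protocol 7.4.1 plans no imputation of missing safety values.

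**The concern.** Once the injection has been given, removal cannot reduce exposure to BI 473494. Its main effect on the data is to shorten observation. The removal reasons include AEs, laboratory or ECG changes, a hepatic alert and interfering concomitant drugs, so the subjects who lose follow-up may be those whose later course is most informative. In a first-in-human trial with six active subjects per dose group, one shortened record carries weight.

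Three things are at stake: later or different AEs in a removed subject, the scheduled ECG and laboratory time course, and AUC0-tz. This last endpoint is defined up to the last quantifiable sample, so its value depends on when sampling stops.

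**Working it through.** **Plan figures.** 11 dose groups × 8 = 88 subjects, which reproduces Protocol 7.6. Day 29 is (29 − 1) × 24 = 672 h after dosing, as in the Flow Chart. No removal or dropout rate is stated.

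**Inputs.**
- End-of-trial examination on Day 33 to 40, i.e. 32 to 39 days after dosing (Flow Chart).
- 16 centrally read post-dose ECG time points: 6, 9, 12, 24, 28, 34, 48, 60, 72, 96, 120, 168, 240, 336, 504 and 672 h (SAP Table 6.7: 1).
- Anticipated median tmax of 16–20 h or, from the monkey study, 32–40 h (Protocol 2.3).
- Half-life: not visible in the documents; assumed 72 to 240 h (3 to 10 days).

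**Follow-up lost.** The share lost is 1 − (removal time / planned window). At 72 h:
- AE window: 1 − 3/32 = 90.6% (29 of 32 days) to 1 − 3/39 = 92.3% (36 of 39 days).
- PK window: 1 − 72/672 = 89.3%.
- ECG: 7 of 16 time points come after 72 h.

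All seven ambulatory visits from 96 to 672 h fall in the lost part, as do the scheduled laboratory days 6, 15, 22 and 29.

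| Removal at | AE window lost | Central ECG points lost | PK window lost |
|---|---|---|---|
| 24 h | 96.9–97.4% | 12/16 | 96.4% |
| 72 h | 90.6–92.3% | 7/16 | 89.3% |
| 168 h | 78.1–82.1% | 4/16 | 75.0% |
| 336 h | 56.2–64.1% | 2/16 | 50.0% |
| 504 h | 34.4–46.2% | 1/16 | 25.0% |
| 672 h | 12.5–28.2% | 0/16 | 0% |

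**AUC0-tz (illustrative).** One-compartment model with first-order absorption: ke = ln 2 / half-life, and ka is solved from tmax = ln(ka/ke)/(ka − ke). AUC(0–T) is proportional to (1 − exp(−ke·T))/ke − (1 − exp(−ka·T))/ka. The ratio AUC(0–72)/AUC(0–672) is:

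| Half-life | tmax 16 h | tmax 40 h |
|---|---|---|
| 72 h | 0.475 | 0.392 |
| 120 h | 0.331 | 0.285 |
| 168 h | 0.262 | 0.231 |
| 240 h | 0.210 | 0.188 |

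The range is 19% to 48%. It takes 672 h as the last quantifiable point in a completer. SAP 4 expects low exposure in the two groups studied. If concentrations fall below quantification earlier, the loss is smaller.

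**Cmax.** In the same model, removal at 72 h loses nothing. Removal at 24 h still captures 91–100% of Cmax, and removal at 12 h captures 64–99%.

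**Primary endpoint.** It counts subjects with at least one drug-related AE. For a subject removed because of a drug-related AE, the count changes by 0. For a subject removed for another reason before a first drug-related AE, the count can be too low by one, which is 1/6 = 16.7 percentage points in an active group of six.

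**The case against.** A reader might infer that selective loss of follow-up biases the primary endpoint toward no effect. The documents do not support that. The endpoint and the AE analyses are per subject (Protocol 5.2.1, SAP 7.8.1), so a subject removed for a drug-related AE is already counted. Only the narrower case in the last step of the working remains.

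A reader might also infer that the removal list was written for repeated dosing and that nothing remains to discontinue. That is not established. Criterion 2 mentions other trial medication, Protocol 4.1.3 has a first administration of trial medication in Visit 2, and Protocol 4.3 refers to non-investigational products. The surrounding text is partly blacked out. The list may have a real function between Visit 2 and the injection, and a later administration of another product cannot be excluded. The point therefore concerns only BI 473494 and the period after its injection.

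Four further objections have force:
- Removal under criterion 4 is a judgement, and symptomatic treatment is allowed (Protocol 4.2.1), so an event does not by itself remove a subject.
- Existing AEs are followed up, and clinically relevant abnormal values are monitored (Protocol 5.2.2.2, 6.2.4). Hepatic alerts follow a checklist. The gap is new non-serious events and the scheduled time course.
- No text says that ECG and PK sampling stop. This is inferred from silence and from the content of the end-of-trial examination.
- The PK exclusion reasons are an open list, the Report Planning Meeting decides on the PKS, SAP Table 6.2: 1 has a missing-data category, and a sponsor SOP that is not visible governs missing PK data. A truncated AUC0-tz may be excluded, but the plan does not say that it will be.

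Finally, 72 h is a chosen scenario. Nine of the 16 ECG points are recorded by then, and PK is now descriptive in two low-dose groups (SAP 4).

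**Conclusion.** The point holds in a limited form. The early end-of-trial examination, the end of CRF collection for new non-serious AEs and the closing of the on-treatment window are all written. The end of the remaining ECG, laboratory and PK schedule follows because nothing continues it.

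The size depends on when removal occurs, and its frequency cannot be derived from the documents. More than half of the AE window is lost for removals up to about Day 17 to 20, and more than half of the PK window for removals before Day 15. Most ECG points are lost only for removals at or before 48 h (9 of 16 lost at 48 h).

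The main loss is later or different AEs, the safety time course and AUC0-tz. Cmax is mostly captured if removal follows tmax. The AUC0-tz range rests on the assumed half-life, the one-compartment model and quantifiable concentrations to 672 h.

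**What to change.** Leave the removal criteria and all clinical decisions as they are. Reconcile Protocol 3.3.4.1 and 6.2.4 with the single-dose design by separating stopping treatment from stopping assessments:

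- After the BI 473494 or placebo injection, a subject who has not withdrawn consent and is able to attend continues the already scheduled AE questioning, ECG, laboratory and PK assessments through Day 29. The end-of-trial examination stays on Day 33–40.
- The early end-of-trial examination is kept for subjects who withdraw consent or cannot attend. This respects criterion 3, which covers subjects no longer able to participate.
- In SAP 6.3, state that AUC0-tz from a subject whose sampling stopped early is listed but flagged as excluded from descriptive statistics.

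The cost is wording in both documents. The visits are already in the schedule. A few subjects attend visits they would otherwise have skipped, and a few AUC0-tz values leave the summary, which is noticeable with six active subjects per group. The SAP sentence applies even though dose escalation has stopped.
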